## **Variables**

At the enrolment visit, demographic data, medical history and concomitant diseases, prior and concomitant medication, risk factors for osteoporosis, and Yselty® dosing regimen will be collected. At baseline, date of first Yselty® dose will be collected.

The variables to assess the primary endpoint, which will be collected at the enrolment visit (recommended only in patient at high risk of osteoporosis or bone loss) and at follow-up visit(s) are:

- BMD z-score measured in lumbar spine, total hip, or femoral neck
- Date of DXA scan, if performed
- Anatomic site of DXA scan, machine type, imaging parameters of DXA scan, and reference population used, if available

The variables to assess the exploratory endpoints will be collected at the enrolment visit and at follow-up visit(s).

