## 8 Research Question and Objectives

Data in patients taking Yselty® in the real-world setting and for more than 1 year is needed to better understand certain safety parameters associated with long-term use. The overall study aim is to assess the long-term safety of Yselty® when used in real life clinical practice.

The primary objective is:

- **I.** To evaluate routinely collected data on long-term safety (>12 months) in relation to BMD with use of Yselty® 200 mg (with ABT) and 100 mg (with and without ABT) dosing regimens.

The exploratory objectives are:

- **II.a** To evaluate the incidence of osteoporosis or fractures suspected to be due to osteoporosis
- **II.b** To evaluate liver enzyme levels above the upper limit of normal and correlated events collected as part of clinical practice
- **II.c** To evaluate any routinely collected clinical data on mood disorders
- **II.d** To evaluate the incidence of uterine endometrial and mammary gland adenocarcinoma
- **II.e** To describe treatment patterns for Yselty® dosing regimens with and without ABT
- **II.f** To evaluate patient adherence to Yselty® treatment
- **II.g** To evaluate any routinely collected clinical data on cardiac disorders indicative for QT interval prolongation
- **II.h** To assess if physicians who prescribe Yselty® follow the summary of product characteristics (SmPC) recommendations including performance of annual dual-energy X-ray absorptiometry (DXA) scans and adherence to the requirement of not prescribing the Yselty® 200 mg regimen without concomitant ABT
- **II.i** To evaluate the incidence of adverse drug reactions (ADRs), serious adverse drug reactions (SADRs) and pregnancies (including pregnancy follow-up)
- **II.j** To evaluate BMD change in patients with routinely collected DXA scans at multiple timepoints to assess mean change of BMD z- and t-scores from baseline or 12-month assessment during long-term (>12 months) use of Yselty®.

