  - Incidence rate of adverse events regarding electrocardiogram (ECG) findings indicative of QT interval prolongation, according to the physician's information
- For objective **II.h**:
  - Frequency of use of DXA scans in defined time periods:
    - Among patients with >1-year treatment, the number and proportion of Yselyt® users who received at least 1 DXA scan between 10 months until 14 months
    - Among patients with >2-year treatment, the number and proportion of Yselyt® users who received at least 2 DXA scans between 10 months until 26 months
    - Among patients with >3-year treatment, the number and proportion of Yselyt® users who received at least 3 DXA scans between 10 months until 38 months
    - Among patients with ≥4-year treatment, the number and proportion of Yselyt® users who received at least 4 DXA scans between 10 months until end of study
  - Frequency of DXA scans prior to treatment initiation in patients at high risk for osteoporosis or bone loss

---

 Additional analyses on ADRs will be performed.

 The RMP (see 15.1) contains targeted follow-up questionnaires for these events. Physicians who report these events will be asked to fill the corresponding targeted follow-up questionnaire.

 The RMP (see 15.1) contains targeted follow-up questionnaires for these events. Physicians who report these events will be asked to fill the corresponding targeted follow-up questionnaire.

 High risk patients will be identified by their treating physician as described in section 9.2.1.

- Number and proportion of patients who received Yselty® at a dose of 200 mg for more than 6 months without concomitant prescriptions for ABT at suitable time periods (e.g., 3-month intervals)
- For objective **II.i**:
  - Incidence rate of ADRs
  - Incidence rate of SADR
- For objective **II.j**:
  - Mean absolute and relative change in density (g/cm^2) and absolute value and relative change of BMD z-score and t-score from baseline (for patients with baseline DXA scan as per routine clinical practice – per SmPC only recommended for patients at high risk for osteoporosis or bone loss)

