  - Mean absolute and relative change in density (g/cm^2) and absolute value and relative change of BMD z-score and t-score from DXA scan at 12 months (for patients with multiple follow-up DXA scans as per routine clinical practice)

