## **9.7 Data Analysis**

### **9.7.1 Statistical Considerations**

Statistical analyses will be of an exploratory and descriptive nature. All variables will be analysed descriptively with appropriate statistical methods: categorical variables by frequency tables (absolute and relative frequencies) and continuous variables by descriptive statistics (i.e., number of patients, mean, standard deviation, minimum, median, quartiles, and maximum). Continuous variables will be summarised by absolute value and changes from baseline per analysis time point, if applicable.

The sample size and disposition information by analysis time point will be displayed in a frequency table.

Procedures and routines for capturing associated data strongly depend on country specific standards of care, type of healthcare provider, and insurance status of patients. Therefore, missing data in non-interventional research are informative categories indicating coverage of services.

No imputation of missing information will be applied. The number and frequency of patients with missing data will be presented as separate category.

All issues concerning patient data validity, data consistency checks, and permissible data modifications will be described in detail in the DMP. All statistical issues including calculated variables and the proposed format and content of tables will be detailed in the SAP. The SAP will be finalised before study database lock.

Information on the interim analysis is presented in section [9.7.5](#). The final data analysis will be performed after the study has been completed and the database has been declared to be clean.

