BMD will be displayed as absolute and relative change in density ( $\text{g}/\text{cm}^2$ ) and absolute value and relative change of z-scores and t-scores over time by means of summary statistics; e.g., DXA scans performed at baseline (if available) vs. timepoint 1 – 1st year (+/-6 months) after treatment initiation, timepoint 1 – 1st year (+/-6 months) after treatment initiation vs. DXA scans performed at timepoint 2 – 2nd year (+/-6 months), where the measurements are at least 6 months apart. This is continued in the same way for further years if the sample size is at least 5 patients. Changes are only analysed if e.g., the machine types, the location of the scan and other criteria that allow comparability are consistent. A subgroup analysis of t-scores for the subgroup of postmenopausal patients and of z-scores in the subgroup of premenopausal patients will be conducted, if sample size allows. Additionally, patients who experienced BMD decrease during the study but continued to be observed in the study, regardless of the reason for which Yselty® treatment was discontinued, will be investigated as a separate subgroup. This subgroup analysis will include the presentation of both absolute value and relative change of z-scores and t-scores after discontinuation. If the sample size permits, this subgroup will be stratified based on whether alternative treatments administered after discontinuation may also lead to a decrease in BMD (refer to “previous systemic treatments” in section 9.3.3).

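### First-year and later BMD changes are shown in overlapping but differently composed sets of women, so a difference between them may reflect the mix of risk groups rather than a change in the rate of loss

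*Protocol*

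**What the plan says.** Objective II.j has two parts in section 9.1.2. The first is change from baseline in women who had a routine baseline scan, which the protocol notes is "per SmPC only recommended for patients at high risk" for osteoporosis or bone loss. The abstract (Variables) says the same of the enrolment measurement: "recommended only in patient at high risk of osteoporosis or bone loss". The second part is change from the 12-month scan, "for patients with multiple follow-up DXA scans as per routine clinical practice", with no restriction by risk. Objective II.h (section 8) refers to SmPC recommendations "including performance of annual dual-energy X-ray absorptiometry (DXA) scans", and its scan counts in section 9.1.2 cover all users by length of treatment.

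Section 9.7.3.4 presents BMD change over time by example rows: "DXA scans performed at baseline (if available) vs. timepoint 1", then year 1 against year 2, and "This is continued in the same way for further years if the sample size is at least 5 patients". The two scans must be at least six months apart, and there is a technical filter: "Changes are only analysed if e.g., the machine types, the location of the scan and other criteria that allow comparability are consistent". The subgroups named there are menopausal status and women with BMD decrease who stay under observation after stopping treatment. On missing scans, section 9.7.1 states: "No imputation of missing information will be applied".

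**The concern.** Each row uses whichever women have the two scans it needs. Entry to the first row requires a baseline scan, which is recommended by risk status. Entry to later rows does not. High-risk status is defined in section 9.2.1 by factors that bear on bone, such as low-trauma fracture, tobacco, low body weight and corticosteroids, so it may well be related to the yearly change in BMD.

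The rationale in section 7 is that even slow, sustained loss may matter over time. A reader will look down the rows to see whether loss continues, slows or speeds up. If the risk mix shifts between the first row and the next, part or all of that step may be a change in who is measured. Nothing in section 9.7.3.4 keeps the women fixed, splits the rows by osteoporosis risk, or reports the risk mix of each row.

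**Working it through.** **The plan's own figures.** The protocol gives no precision or size for the II.j rows apart from the minimum of 5 patients. Table 2 gives the enrolled numbers under 20% yearly dropout. These reproduce: 1,000 × 0.8 = 800, × 0.8 = 640, × 0.8 = 512, × 0.8 = 409.6 (stated as 409). At the minimum of 5 patients, the 95% CI half-width of a mean is t(0.975; 4)/√5 = 2.776/2.236 = 1.24 SD.

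**Artefact formula.** Let s1 and s2 be the high-risk shares of the baseline-to-year-1 and year-1-to-year-2 rows, and let rH and rO be the yearly changes in high-risk and other women, constant over time in every woman. A row mean is s × rH + (1 − s) × rO. The difference between the rows (second minus first) is (s2 − s1) × (rH − rO). It is zero if the shares are equal or the rates are equal.

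**Assumptions (none is in the protocol).** High-risk share h of the cohort; baseline scan in bH of high-risk and bO of other women; follow-up scan uptake fH and fO; equal attrition in the two groups.

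*Case A: equal follow-up uptake (fH = fO); h = 0.20, bH = 0.80, bO = 0.05, rH = −1.5%, rO = −0.5%.*
- s1 = 0.20 × 0.80 / (0.20 × 0.80 + 0.80 × 0.05) = 0.16/0.20 = 0.80; s2 = 0.20.
- First row: 0.80 × (−1.5) + 0.20 × (−0.5) = −1.30%.
- Second row: 0.20 × (−1.5) + 0.80 × (−0.5) = −0.70%.
- Apparent slowing: 0.60 percentage points, although no woman's rate changes.

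*Case B: as A, but follow-up uptake fH = 0.60 and fO = 0.20.*
- s1 = 0.20 × 0.80 × 0.60 / (0.20 × 0.80 × 0.60 + 0.80 × 0.05 × 0.20) = 0.096/0.104 = 0.92.
- s2 if the same women are rescanned each year: 0.20 × 0.60 / (0.20 × 0.60 + 0.80 × 0.20) = 0.12/0.28 = 0.43.
- s2 if uptake is independent from year to year: 0.20 × 0.36 / (0.20 × 0.36 + 0.80 × 0.04) = 0.072/0.104 = 0.69.
- First row −1.42%; second row −0.93% or −1.19%; apparent slowing 0.49 or 0.23 points.

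*Range with equal follow-up uptake, h = 0.1 to 0.4, bH = 0.80, bO = 0 to 0.20.* High-risk women make up 31–100% of the first row and 10–40% of the second.

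| rH / rO (% per year) | Second row minus first row (points) |
|---|---|
| −1.5 / −0.5 | +0.21 to +0.90 |
| −1.0 / −0.5 | +0.10 to +0.45 |
| −0.5 / −1.0 | −0.10 to −0.45 |
| −0.5 / −0.5 | 0 |

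**Overlap.** Let f be the follow-up uptake per year, equal in both groups and independent between years. The year-1-to-year-2 row then holds 640 × f² women, of whom a fraction h × bH + (1 − h) × bO also have a baseline scan. For h = 0.20, bO = 0.05 and f = 0.5 this is 160 women, of whom 160 × 0.20 = 32 are in both rows. Over h = 0.1 to 0.4, bO = 0 to 0.05 and f = 0.3 to 0.8, about 5 to 143 women are in both rows, out of 58 to 410.

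**Later rows.** Year 1 to 2 and year 2 to 3 do not require a baseline scan. Differences between them can come from attrition and scan uptake, but not from selection into baseline scanning.

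**The case against.** The case for leaving the plan alone has real weight. II.j is exploratory, no trend test or model is planned, and section 9.1.2 openly states the population of each part. The rows in 9.7.3.4 are given as examples, and the baseline-anchored endpoint could itself be followed into later years in women who all have a baseline scan. Section 9.7.2 allows stratification by further clinical characteristics to be named in the SAP, and section 9.7.4 warns about selection and confounding. Much of this could be settled in a SAP that is not at hand. Matched sets may also be too small to say much.

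Most of this lowers the weight of the point without removing it. The protocol does fix a sequence of rows, a minimum n and named subgroups. The stratification in 9.7.2 is conditional and does not name osteoporosis risk. Section 9.7.4 names site and disease severity as possible confounders, and section 9.9 does not mention a shift in composition between intervals.

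A reader might go further and infer that the first-year and later rows come from different women, or that a planned trend analysis is confounded. The documents do not support either reading. High-risk women who keep being scanned appear in both rows, some other women may have a baseline scan, and no comparison of year 1 with later years is specified. Nor do they establish that later rows are mainly ordinary-risk women: section 9.9 says uptake of follow-up DXA is uncertain, and Case B shows high-risk women could form a large part of those rows.

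**Conclusion.** The point holds in a limited form. The first-year row and the later rows are drawn from overlapping sets that are likely to differ in risk mix, and a difference between them cannot be read as a change in the rate of loss unless yearly change is the same in both risk groups. The shift in mix is an expectation from the scanning recommendations; the actual mix depends on uptake.

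No size can be fixed from the protocol. The illustrations run from 0 to 0.90 percentage points in either direction or none, depending on assumed risk share, baseline and follow-up scan rates in each group, and yearly losses. It would be tempting to conclude that the display will look falsely reassuring; that requires high-risk women to lose faster, which the protocol does not state. If they lose more slowly, the rows would suggest acceleration.

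Because the endpoint is exploratory and descriptive, this is an inexpensive improvement to a display that could mislead. It does not undermine the primary analysis.

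**What to change.** In section 9.7.3.4:
- Report for each interval the number of women and the share at high risk.
- Show each interval separately for high-risk and other women. Risk factors are recorded at enrolment (section 9.3.2), and physician-identified high-risk status is already needed for II.h.
- Add a supportive table of women with comparable scans at all time points shown (for example baseline, year 1 and year 2; separately years 1, 2 and 3), where n is at least 5.
- State that first-year and later changes are compared only within risk strata or within these matched sets.

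In the constant-rate illustration, either the split or the matched set brings the composition artefact to zero by construction. The cost is one stratification factor and one further table, with no new data. The downside is small strata and small matched sets, with wide intervals; the comparability filter and any split by dosing regimen would shrink them further. Even then, n and the high-risk share per row can still be reported and tell the reader how far the rows are comparable.

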#### **Follow-up visit(s) for patients who experienced BMD decrease or osteoporosis during the study**

Patients who discontinued treatment with Yselty® but had BMD decrease or osteoporosis during the study should be observed in the study for up to 24 months after the last administration of Yselty®. Documentation of further visits by the physician during the further follow-up period will be limited to BMD assessments and relevant concomitant medications. For AE reporting please see section 11.3.

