### **Final visit/End of observation period**

The final data collection (last visit) is at the end of study (regular end of study or after further follow-up for patients with BMD decrease or osteoporosis) or at discontinuation of Yselyt® therapy for patients without BMD decrease or osteoporosis (whatever is earlier). At this final observation point, the patient's condition and a treatment assessment will be documented as a follow-up visit with additional information on:

- Regular end of observation, or
- End of observation after further follow-up for patients who discontinued Yselyt® treatment but had a BMD decrease or osteoporosis (see section above) during the study, or
- Discontinuation of follow-up with the reason for discontinuation (e.g., end of therapy with Yselyt® and no BMD decrease or osteoporosis).

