### **9.5 Study Size**

Approximately 1,000 women of reproductive age with documented uterine fibroids and symptoms such as HMB being treated with Yselyt® long-term, according to the SmPC. This is a multinational study in 5 European countries (Germany, Italy, Spain, Poland and UK), whereas the selection and sequence of countries may change depending on the launch dates of Yselyt®. The number of study sites will vary per country, dependent on use of Yselyt®.

This is a descriptive study and is not intended to test a formal hypothesis. The sample size is based on feasibility and practical considerations rather than statistical. Sample size considerations are based on the primary endpoint, BMD z-score, which compares bone mineral density with a reference population of the same age and sex. The BMD z-score will

---

 Special situations include drug interactions, medication abuse, medication misuse, medication overdose, medication errors, unexpected therapeutic or clinical benefit from product use, pregnancy or lactation exposure with the product, lack of efficacy, off-label use, and occupational exposure (see section 11.4).

be measured at 3 sites for each patient, i.e., lumbar spine, total hip, and femoral neck and the lowest individual value is used to estimate the population proportion.

A single-group design was used to obtain a 2-sided 95% confidence interval (CI) for a single proportion. Given the standard normal distribution of BMD z-scores (z-distribution), the expected sample proportion of values < -2 (cutoff for low bone density) is assumed to be 2.5%, which corresponds to the lower 2.5% quantile of the z-distribution. With an effective sample size of 800 (assuming 20% dropout), the CI width at 12 months of follow-up is 2.2% and the expected precision of the proportion is 2.5%±1.1% (see Table 2). Assuming a further 20% yearly dropout rate, at 24 months of follow-up, the effective sample size is estimated to be 640 patients with a CI width of 2.4% and an expected precision of the proportion of 2.5%±1.2%. At 36 months of follow-up, the effective sample size is estimated to be 512 patients with a CI width of 2.8% and an expected precision of the proportion of 2.5%±1.4%. At 48 months of follow-up, the effective sample size is estimated to be 409 patients with a CI width of 3.0% and an expected precision of the proportion of 2.5%±1.5%.

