## **9.9 Limitations of the Research Methods**

Possible limitations of the study are based on the observational design and the fact of voluntary participation of physicians and patients. Physicians and patients who voluntarily agree to participate in this study might differ from those who do not agree. Consecutive enrolment should avoid any selection bias and increase the likelihood of representativeness.

Although the study aims to include participants from a variety of geographic regions, there may be local limitations that reduce the representativeness of patients recruited, such as

patient access to recruiting physicians (including differences in patient profile in specialized, recruiting sites vs local general practice), Yselty® availability and reimbursement, and decisions relating to local standard of care.

The main objective depends on two factors that are crucial but beyond the control of the study: First, the overall uptake of Yselty® and the proportion of patients treated beyond 12 months. Second, the extent to which doctors perform DXA scans after 1 year (as recommended in the SmPC) as part of their routine care. Depending on the country, this could be either facilitated or hindered by the reimbursement status of DXA scans.

BMD measurements, the primary objective, have a good reproducibility under highly controlled conditions, but such conditions do not generally apply in clinical practice. Many factors could affect the accuracy of BMD testing, including inter-machine variance as well as the experience of the operator. In addition, a high rate of missing BMD measurements at week 24 and week 52 due to study discontinuations was observed in the two pivotal studies [11]. This indicates that BMD assessment may become difficult due to the low number of observations recorded, especially for long-term users which are of special interest in this study. When interpreting the proportion of patients with z-scores below -2 standard deviations indicating loss of bone density, it should be kept in consideration that normalisation of z-scores is usually based on BMD measurements for a single bone. If multiple measurements have been taken in a patient, the likelihood of results being below threshold increases with the number of bone sites examined for each patient.

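### Following and analysing only women with a measured BMD decrease after they stop treatment builds regression to the mean into the change after discontinuation, in a direction set by a reference scan the protocol does not name

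*Protocol*

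**What the plan says.** Three parts of the protocol act together.

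- **Who is followed after stopping (9.2.6, follow-up for patients with BMD decrease or osteoporosis).** Women who stop treatment and "had BMD decrease or osteoporosis during the study should be observed in the study for up to 24 months after the last administration of" the product. For women with neither, the final-visit paragraph of 9.2.6 ends data collection at discontinuation. Table 1 (footnote 10) and section 11.3 repeat the same condition. None of these places gives a size, a bone site or a pair of scans for the decrease.
- **Who is analysed (9.7.3.4).** A separate subgroup is formed of "patients who experienced BMD decrease during the study but continued to be observed in the study, regardless of the reason" for stopping.
- **What is shown (9.7.3.4).** "This subgroup analysis will include the presentation of both absolute value and relative change of z-scores and t-scores after discontinuation". The scan from which that change is measured is not stated.

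On measurement error, 9.9 says: "BMD measurements, the primary objective, have a good reproducibility under highly controlled conditions, but such conditions do not generally apply in clinical practice". It gives no precision figure. The protocol gives no expected result for this subgroup.

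**The concern.** A woman enters the subgroup because one scan read lower than an earlier one. Part of any such difference is scan error. If the off-treatment change starts from the low scan, the error that helped select her is absent, on average, from her next scan, so her reading rises even if her bone does not. Women whose error ran the other way would show the opposite movement, but unless they had osteoporosis they leave the study at discontinuation, and in any case they are outside this subgroup. Nothing in the table offsets the shift.

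This is more than an undefined term. The selection and the subgroup-only summary produce the bias whatever size of decrease is later chosen.

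At stake is how the off-treatment BMD data will be read. Sections 4 and 7 make BMD loss the safety concern of particular interest, and this subgroup is the only planned presentation of BMD change after stopping. On the natural reading, it overstates the loss in the selected women and then shows part of that overstatement as recovery.

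**Working it through.** **Inputs from the protocol.** Selection is on a measured decrease with no stated limit (9.2.6, 9.7.3.4). Women without a decrease or osteoporosis have no off-treatment scans (9.2.6). BMD is to "be measured at 3 sites for each patient, i.e., lumbar spine, total hip, and femoral neck" (9.5). Changes are analysed only between comparable scans (9.7.3.4), which limits machine and location differences but does not remove random error on one machine.

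**Assumptions (not in the protocol).** Error SD s per scan is 1–2% of BMD, normal and independent between scans. The true on-treatment loss has mean L and between-woman SD τ. True off-treatment recovery is zero. Decrease is read as any fall, cut-off c = 0.

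**Model.** X0 is the earlier scan, X1 the on-treatment scan that qualifies the woman, X2 the off-treatment scan. A woman qualifies if X1 − X0 < −c. Let D = √(2s² + τ²) and a = (L − c)/D. With φ and Φ the standard normal density and distribution function:

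- share qualifying = Φ(a)
- false recovery from the qualifying scan = E[X2 − X1 | qualifies] = (s²/D) · φ(a)/Φ(a)

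**No true loss** (L = 0, τ = 0, c = 0). D = 1.414s and a = 0, so φ/Φ = 0.798. The false recovery is 0.798s/1.414 = 0.564s, that is 0.56%, 0.85% and 1.13% of BMD for s = 1, 1.5 and 2%. The apparent on-treatment fall is twice that (1.13–2.26%), so half of it seems to return.

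**With true loss that does not recover** (c = 0):

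| Mean loss L (SD τ) | s = 1% | s = 1.5% | s = 2% |
|---|---|---|---|
| 1% (1%) | 0.27 | 0.53 | 0.80 |
| 2% (1.5%) | 0.14 | 0.33 | 0.56 |
| 3% (1.5%) | 0.07 | 0.20 | 0.39 |

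Example, L = 1, τ = 1, s = 2: D = √(8 + 1) = 3, a = 0.333, φ/Φ = 0.5985, giving (4/3) × 0.5985 = 0.80. Simulation of 1,000,000 women agrees to within 0.01.

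**Stricter cut-off**, c = 2.77s. With L = 0 and τ = 0, only 2.5% qualify, but the false recovery is 1.65s (1.7–3.3%). With L = 1, τ = 1 it is 0.9–2.6%. With L = 2, τ = 2 it is 0.4–1.8%.

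**Other reference scans.** From the earlier scan X0, the bias is −(s²/D) · φ(a)/Φ(a): the same size with the opposite sign (−0.56s with no true loss). From a scan that played no part in selection, it is zero (simulated 0.001s).

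**Using all women.** Regressing X2 on X0 and X1 in the women followed, then averaging the prediction over all women, is the likelihood estimate for this pattern of missing data. In simulation it gave a recovery of 0.00 (within ±0.02) in every scenario without a cut-off.

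**On the planned scale.** For z-scores rounded to 0.1, one site and one re-scan, with assumed noise of 0.10–0.20 z, 37–43% qualify on noise alone and the false rebound is 0.08–0.13 z.

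**The case against.** The strongest reply is that the bias depends on choices the protocol has not made. It speaks of a decrease, never of any decrease, and the SAP may define it. Section 9.7.3.4 names no reference scan: a woman whose fall was seen at year 1 and who stopped at year 3 could have a later on-treatment scan as her start, with no bias. This stands, and three stronger readings that a reader might infer fail:

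- **That the plan as written necessarily errs towards reassurance.** The direction depends on the unnamed reference scan.
- **That scan noise alone puts at least half of re-scanned women in the subgroup.** That needs any fall to count, no true gain and unrounded density. Rounded z-scores give 37–43% at one site.
- **That reversibility is the only purpose of the extended follow-up.** Section 11.3 also uses it to collect adverse events associated with BMD loss and all adverse drug reactions. No objective in section 8 names reversibility.

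It is also fair that the study is descriptive, that 9.7.4 asks for cautious interpretation, and that 9.9 concedes limited DXA accuracy and few observations. These reduce the risk of over-reading, but neither section mentions selection on a measured fall.

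Against a model, scans follow physician discretion and reimbursement, so missing-at-random is not assured, and the off-treatment course of women without a decrease would be largely extrapolated. Restarting from a later scan has its own cost: with roughly annual visits and at most 24 months of follow-up, that scan may already be off treatment and miss early recovery. These points make the model supplementary and the later start a sensitivity analysis. They do not rescue the subgroup table.

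**Conclusion.** The concern holds in this form: selection on a measured fall, followed by a summary in the selected women alone, gives a biased off-treatment change whenever the reference is one of the two scans that defined the fall. From the qualifying scan, the apparent recovery is 0.56–1.13% of BMD with no true loss and about 0.07–0.80% with a true mean loss of 1–3%. From the earlier scan, the bias is equal and opposite.

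The sizes rest on an assumed scan error SD of 1–2%, normal independent errors, any fall counting as a decrease, and no true recovery. The bias is small when true loss is large against scan error, and continuing true loss could mask it. Tightening the definition lowers the number selected by noise but enlarges the false rebound in those who qualify. The analysis is exploratory and the primary endpoint is unaffected, so the change is advisable but not critical.

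**What to change.** In 9.7.3.4, with detail in the SAP:

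1. Name the reference scan. Where both are available, show the off-treatment change from the qualifying scan and from the earlier scan that defined the fall, and state that the first overstates and the second understates recovery.
2. Add a supplementary likelihood-based longitudinal analysis of density in g/cm², using all comparable on- and off-treatment scans of all patients, with separate on- and off-treatment time terms. Base any statement on reversibility on it. State that it assumes missing at random and that the off-treatment course of women without a decrease is largely model-based.
3. As a sensitivity analysis only, start the change from a scan that played no part in selection, and note that this may miss early recovery.

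The descriptive subgroup table stays, and neither the follow-up rule nor data collection changes. The cost is about one paragraph, one further model on data already planned, one added assumption in a descriptive study, and a recovery estimate that will be smaller and less precise.
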